VERSION DATE APRIL 22, 2016

TITLE: A comparison of early deployment of a video capsule (Endocapsule EC-10: Olympus Tokyo. Japan) in the Emergency Department versus conventional work-up of non-hematemesis gastrointestinal bleeding [NHGIB].

NCT02442830

[name], PHD, PRINCIPAL INVESTIGATOR

INVESTIGATOR STUDY PLAN - REQUIRED

1) Title

A comparison of early deployment of a video capsule (Endocapsule EC-10: Olympus Tokyo. Japan) in the Emergency Department versus conventional work-up of non-hematemesis gastrointestinal bleeding [NHGIB].

2) IRB Review History*

Not applicable.

3) Objectives*

The objectives of this study are to test whether there are statistically significant differences between the conventional workup of NHGIB by endoscopy [upper, lower and other tests], compared with deployment of a video capsule VCE as the first test followed by the most appropriate endoscopic procedure based on VCE findings, if needed. We propose to examine differences in time to diagnosis, reduction in numbers of procedures, and length of stay between a conventional workup protocol and our proposed protocol of early capsule endoscopy deployment.

4) Background*

After 40 years of considering gastrointestinal bleeding as upper or lower and largely ignoring the small intestine, there is accumulating evidence that the conventional approach to the assessment of NHGIB could be improved by early deployment of a video capsule as the first diagnostic test. Currently, video capsule endoscopy is considered the gold standard as the diagnostic test for small intestinal bleeding. In a recent study at UMass of 336 patients who presented to the ED with complaints of gastrointestinal bleeding 36 patients (10.7%) were given a video capsule during their stay.¹

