In patients with hematemesis, upper endoscopy remains the diagnostic and therapeutic modality of choice. However patients with melena and hematochezia may benefit from early VCE since both signs and symptoms provide poor localization as to the origin of bleeding. Data from our previous study suggests that the ingestion of a video capsule in the emergency department could quickly and non-invasively provide clinicians accurate data as to the origin of the bleeding. This information could provide a guide to further management of the patient. Video capsule endoscopy is able to visualize bleeding in the esophagus, stomach, duodenum, small intestine and right colon, thereby eliminating the guess work of deciding which endoscopic approach to use.

At UMass, we have shown that of the 36 patients who received a video capsule, 26 (72.2%) had diagnostic studies (i.e. bleeding was identified). In comparison, 152 patients required upper endoscopy (of which 52.9% were diagnostic) and 64 patients required colonoscopy (of which 47%

INVESTIGATOR STUDY PLAN - REQUIRED

were diagnostic). Of those 26 patients with diagnostic capsule studies, 13 also required upper endoscopy, 1 required a colonoscopy, and 4 required both a colonoscopy and endoscopy. It is important to recognize, however, that often capsule studies are performed AFTER upper endoscopy and colonoscopy and performed and are negative. This sequence is the conventional work up of bleeding. Despite being performed later in the hospital course of our patients, capsule studies have a high diagnostic yield. In reality VCE is used uncommonly in acute bleeding because it is rarely considered in the context of acute GI bleeding

In this study, we propose the approach of using the video capsule as the first diagnostic test PRIOR to colonoscopy and endoscopy; this may lead to a shortened time to diagnosis, a reduction in length of stay, and a reduction in numbers of procedures due to early, accurate localization of the source of bleeding. All of these components could result in better quality of care and cost containment.^{1,2} Further, it is known that 80% of patients stop bleeding spontaneously. Thus the earlier they are examined the more likely the origin of the bleeding is likely to be found

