Once a subject is identified a page will be sent to a member of the research team (i.e. ED screener, research staff member, GI fellow on call, or GI attending on call) from the ED. In addition to this, the clinical research coordinator and or GI fellow will screen the Emergency Department triage software for patients who are listed as having NHGIB. Based on prior experience Ref Sachdev we expect for every 3 patients asked to participate in the study, there will be 1 patient who agrees to participate. In the emergency department study already cited, the Emergency Department at UMass sees about 350 patients annually for GI bleeding. Of these patients, approximately 230 patients have NHGIB. Given the 3:1 screening ratio, we would expect approximately 75 NHGIB patients every year to agree to participate in the study. In 24 months, we would expect to recruit up to 160 patients to our study.

INVESTIGATOR STUDY PLAN - REQUIRED

Once a subject is identified the subject will then be seen and examined by the GI fellow and attending as per standard of care and asked to participate in the study

Randomization

If inclusion/exclusion criteria are met, the consent discussion takes place and only if the subject agrees and consent is obtained, then the subject is randomized to the “Early Capsule Group” or “Conventional workup Group.” All patients in the “Early Capsule group” will receive the video capsule. Only some of the patients in the “Conventional Workup Group” will receive the capsule as indicated by what is considered the standard workup.

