We will assign patients to study ID numbers consecutively by the order of which they are enrolled in our study. For the Randomization Process we will be utilizing a random sorting generator to assign integers in a random order, corresponding to study IDs which allows researchers to randomly assign study participants into specific study groups. Assignments are put into a mail merge, locked with a password, and printed, then put into a sealed, security envelope, which is sealed with a Study ID sticker. The Randomization Scheme will allow us to attach particular Study ID numbers randomly to particular groups based on our criteria to have 80 subjects in the early capsule group and a comparable number in the conventional workup group. The envelope is only opened once all entry criteria have been met and the subject will be assigned a group. Subjects with a Study ID ending in 1-100 will be enrolled at University Campus. Subjects with a Study ID ending in 101-120 will be enrolled at Memorial Campus. Subjects with a Study ID ending in 121-160 will be enrolled at either campus, depending on enrollment. Enrollment will be competitive at the two locations and there is no specific quota to be reached at either location.

We plan to enroll up to 160 subjects in our study. 80 subjects will be randomized to the “early capsule” deployment group. This means that this group of subjects will have a VCE deployed as soon as possible after presentation to the ED, once the consent process has taken place, eligibility has been confirmed, and the subject has met the standard of care guidelines for preparation before capsule ingestion. Standard preparation for capsule ingestion means that a patient cannot eat for 10 hours prior to deployment of the capsule. Therefore, patients in our study will be asked when they had last eaten. If patients report that they have not eaten anything over the past 10 hours we will deploy the capsule immediately. If, however, patients say that they have eaten something over the past 10 hours we will take note of when they believe they last ate and will deploy the capsule 10 hours after the time that they last ate. In the pilot [Sachdev] study all patients in the early capsule arm received the capsule within a mean of 4 hours of admission to the ED, and none had food in the stomach on capsule examination.

INVESTIGATOR STUDY PLAN - REQUIRED

Procedure

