Throughout course of a study subject's participation in the study they will be followed for signs of adverse events to medication administration or for complications of capsule endoscopy. Adverse events will be documented as part of initial data analysis. This data analysis will be performed by the residents and fellows who are part of the study staff for this project.

Given that we anticipate minimal adverse events, any adverse events that occur will be reviewed by the study staff and the Primary Investigator within one week. This would include a complete analysis of the how the adverse event occurred in order to help prevent further events going forward. At that time the Primary Investigator will also assess cumulative reports.

14) Withdrawal of Subjects*

If the patient is unable to swallow the capsule we would remove them from the study.

Patients will be withdraw from study if the bleeding source is found to be outside of the stomach or intestines.

A subject can withdraw from the study at any time per their request.

15) Risks to Subjects*

This study is investigating the benefits of re-ordering the process of the current care algorithm for NHGIB. Video capsule endoscopy is already part of standard of care for many GI bleeding workups. This is not a new diagnostic modality and no new risk is being introduced from this technology itself. There are no anticipated risks to subjects who are randomized to the early deployment of the capsule and the diagnostic yield is expected to be at least comparable to the standard deployment.

One anticipated risk is a breach of confidentiality and to minimize this risk all identifiers will be destroyed. In order to minimize this risk, as described in question 12, identifiers will be destroyed. Data collected will be analyzed using study ID numbers only.

The most significant risk of VCE is capsule retention. This risk is the same for both groups and there is no anticipated unforeseen risk with early deployment. The risks do not change based on timing. Capsule retention is when the video capsule does not complete its transit throughout the GI tract. Studies have varied in their reports of the frequency of capsule retention with rates of about 1%, ranging from 1-13% of total cases. The

INVESTIGATOR STUDY PLAN - REQUIRED

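### Section 14 removes some patients after randomization, and neither the protocol nor the SAP says they stay in the analysis; the direction of any bias is unknown and its likely size is small

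*Protocol*

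**What the plan says.** Protocol section 10 (Randomization) puts consent and eligibility before assignment: "The envelope is only opened once all entry criteria have been met and the subject will be assigned a group". Every early-arm patient is then to be given a capsule, while in the conventional arm only some patients "will receive the capsule as indicated by what is considered the standard workup".

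Section 14 lists three ways out of the study:

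- the swallowing rule: "If the patient is unable to swallow the capsule we would remove them from the study";
- the source rule: "Patients will be withdraw from study if the bleeding source is found to be outside of the stomach or intestines";
- the patient's own choice: "A subject can withdraw from the study at any time per their request".

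The third is an ordinary right and is not at issue. Section 14 is silent on what happens to the data of patients who leave under the first two rules.

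The analysis text does not fill the gap. Section 12 compares two cohorts, and the SAP (Statistical analysis) compares two groups by Kaplan-Meier and log-rank. Neither names an analysis set or says whether removed patients are kept, censored or replaced.

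Three other places bear on the size of the problem. Section 5 excludes patients with dysphagia. Section 28 acknowledges that a patient may be unable to swallow the device but gives no rate. Section 10 (Review and Follow-Up) equates diagnosis with localizing the source, and the SAP makes localization the primary outcome.

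**The concern.** Randomization protects the comparison only if the groups analysed are the groups assigned. Both rules depend on something learned after assignment.

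The swallowing rule is asymmetric. A patient who cannot swallow the capsule is discovered only when a capsule is offered, which happens to everyone in one arm and to a minority in the other. The matching conventional-arm patients are mostly never identified and remain in.

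The source rule can act in either arm, but it conditions on where the source is found. That is tied to the endpoint in both documents, and the two arms look for the source by different test sequences.

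If either rule is applied as an exclusion, the estimated difference mixes the effect of the strategy with the effect of who was removed. If the matter stays unspecified, the choice can be made once results are known.

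**Working it through.** **Base.** The SAP's 36 per group can be reproduced and is not disputed. Freedman's formula for a hazard ratio of 2, two-sided 5% (sidedness assumed) and 80% power gives (1.960 + 0.842)² × ((1 + 2)/(1 − 2))² = 7.85 × 9 = 70.6, so 71 events. That agrees with 72 patients if all of them are localized.

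**Who is removed for not swallowing.** If a share u of conventional patients is offered a capsule and failure per attempt is equal (assumed), the early-arm share of removals is 1/(1 + u). The documents give only proxies for u:

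- Section 10 estimates that 5–15% of patients bleed from the small intestine.
- Section 4 reports that, of 336 patients with GI bleeding, "36 patients (10.7%) were given a video capsule during their stay"; 36/336 = 10.7% reproduces.
- Section 10 says that, of about 350 GI bleeds a year, "approximately 230 patients have NHGIB". If all 36 capsules went to such patients, u = 36/(336 × 230/350) = 36/220.8 = 16.3%.

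For u = 5%, 10.7%, 15% and 16.3%, the early-arm share is 95%, 90%, 87% and 86%. Even at u = 50% it is 67%.

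**Shift in the early-arm rate.** Assume 22 of 36 localized (about 60%). Remove k patients, of whom a fraction q would have localized. The shift is (22 − kq)/(36 − k) − 22/36.

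| q | k = 1 | k = 2 | k = 3 |
|---|---|---|---|
| 0 (upper bound) | +1.7 | +3.6 | +5.6 |
| 0.3 | +0.9 | +1.8 | +2.8 |
| 0.5 | +0.3 | +0.7 | +1.0 |
| 22/36 | 0 | 0 | 0 |
| 0.8 | −0.5 | −1.1 | −1.7 |

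The values are percentage points. For example, k = 3 and q = 0.8 gives 19.6/33 − 22/36 = 59.4% − 61.1% = −1.7. The q = 0.5 row is close to the endoscopy yields in section 4 (52.9% upper, 47% colonoscopy); the other rows rest on no document figure. With 48 of 80 localized and 4 removed, q = 0, 0.3, 0.5 and 0.8 give +3.2, +1.6, +0.5 and −1.1.

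**Effect on the log-rank test.** These are simulations with no true difference, 36 per arm and 60% localized. The upper tail, favouring early capsule, is 2.5% with none removed. For k = 1/2/3 it is:

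- 2.7/2.9/3.1% at q = 0.5;
- 3.1/3.6/4.2% at q = 0.3;
- 3.5/4.7/6.2% at q = 0;
- 2.3/2.0/1.7% at q = 0.8.

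Total two-sided error moves less, because error passes from one tail to the other. It is 5.1% with none removed, then 5.2/5.1/5.2% at q = 0.5, 5.2/5.3/5.5% at q = 0.3 and 5.1/5.6/6.7% at q = 0.

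**Source rule.** The sign depends on how removed patients are classified under the SAP definition. From a base of 22 of 36, removing 1 or 2 who count as localized gives 21/35 or 20/34, which is −1.1 or −2.3 points for that arm. Removing 1 or 2 who do not count gives 22/35 or 22/34, which is +1.7 or +3.6. Equal removals of like patients in both arms leave the difference unchanged at equal base rates.

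**The case against.** The strongest case against is that this is an omission with little practical effect. Section 14 may mean only that participation ends; nowhere do the documents say that data will be discarded. Dysphagia is screened out, no removal rate is given, and ordinary endoscopy remains open to a patient who cannot swallow a capsule. In the one scenario close to document figures (q = 0.5), the shift is at most 1 point and total two-sided error barely moves. All of this stands, and it limits the size of the point. It does not remove it: followed literally, section 14 takes randomized patients out of the study, and nothing elsewhere puts them back into the analysis.

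A reader might infer that the swallowing rule biases the trial towards early capsule. The documents do not support that. They say nothing about how non-swallowers localize. Removal favours early capsule if those patients would have localized less often or later than the rest, and works against it if more often or sooner. Uneven removal between arms is well supported; the direction of bias is not.

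A reader might also infer that the source rule lowers the rate in the arm where more such sources are found. That holds only if those patients count as localized. The SAP requires blood or a lesion with high-risk stigmata and analyses endoscopic localization, so a source outside the gut may not qualify.

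Finally, section 10 treats blood in the esophagus as a finding that directs the next test, whereas the source rule read literally would withdraw an esophageal source. One passage concerns where blood is seen and the other where the bleeding originates, so this is loose wording rather than a firm contradiction.

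**Conclusion.** The point holds as a gap in the analysis rules that should be fixed. Two stated rules act after assignment, one mostly in the early arm and one on a finding tied to the primary outcome, and no text keeps these patients in the analysis. This much rests on the documents alone.

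The direction of bias is unknown for both rules. The size is probably small: about 1 point or less in the early-arm rate if half of the 1–3 removed patients would have localized, and +5.6 points as the extreme with three removed and none localizable. These figures rest on an assumed removal count, an assumed localization rate near 60% and assumed outcomes in those removed. The 86–95% share rests on proxies for conventional-arm capsule use and on equal failure per attempt. It would go too far to conclude that the documents prescribe exclusion or that the result will favour early capsule.

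**What to change.** State in section 14 and in the SAP that the primary analysis includes all randomized patients in their assigned arm. Patients who meet either rule stay in the denominator. Their localization is counted at its actual time, under the SAP definition applied identically in both arms. Record review and the planned 3-day and 30-day telephone calls continue unless the patient withdraws consent for them. Report removals by arm with reasons, and show exclusion under section 14 only as a sensitivity analysis. This concerns the analysis set and data collection; it need not change what the withdrawal rules mean clinically. The wording on esophageal findings in sections 10 and 14 should be reconciled.

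The cost is a few sentences and a few more calls. In-hospital data already come from record review. The SAP is dated June 2018 and written in the past tense, so further calls may no longer be possible; the analysis set and the report by arm would then still be worth stating.

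There is also some loss of power if non-swallowers follow the conventional-arm course. At a hazard ratio of 2, 36 per arm and 91% localized (assumed, and a different scenario from the 60% used for bias), simulated log-rank power falls from 0.80 to 0.77 with one such patient and to 0.73 with two. For the protocol's time endpoint, if such patients take the conventional mean time, the planned 14.1 h difference becomes 14.1 × (1 − k/80), which is 13.9, 13.7 or 13.4 h for k = 1, 2 or 4. That is immaterial.

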The use of capsule endoscopy has been approved by the FDA since 2001 for small intestinal bleeding obscure GI Bleeding]. It is very safe, no deaths associated with its use have been reported. More than two million capsule have been used and obstruction and perforation are extremely rare.

Interest in the broader use of VCE is accumulation. In 2004 Sachdev et al reported a pilot study on the use of early use of VCE in acute NHGIB. This showed a 50% reduction to time to diagnosis in 24 patients. More recently studies of VCE deployed in the ED, in patients with upper GI bleeding showed improved management. Our group recently demonstrated that the closer a video capsule is performed to the time of bleeding the higher the likelihood of locating the sources and the higher the therapeutic intervention rate.³ We also have demonstrated that the use of capsule endoscopy in patients with NHGIB has a higher diagnostic yield than does colonoscopy. With improved diagnostic yields, capsule endoscopy may help clinicians by providing guidance in the management of patients with NHGIB.

This protocol is be the first attempt to prospectively examine this concept in a large randomized prospective trial. The questions are, can early capsule intervention decrease time to diagnosis, numbers of procedures and hospital length of stay in patients with non-hematemesis gastrointestinal bleeding.

References:

1. Jawaid S GB, Singh, A, Marshall C, and Cave D. . The epidemiology of gastrointestinal bleeding in an academic emergency department as a basis for

INVESTIGATOR STUDY PLAN - REQUIRED

reconfiguring the conventional approach to its diagnosis and management. .
Gastrointestinal Endoscopy 2013;77:Supplement, Page AB483.

5) Inclusion and Exclusion Criteria*

Inclusion Criteria:

- Age greater than 18 years old
- New onset of melena or hematochezia
- Able to sign consent
- Hemodynamically stable (i.e. blood pressure >100/60 or pulse <110 at the time of consent)

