- ED must plan to admit patient to the hospital or Clinical Decision Unit.

Exclusion criteria:

- Adults unable to consent
- Individuals who are not yet adults (infants, children, teenagers)
- Pregnant women
- Prisoners
- Prior history of gastroparesis
- Prior history of gastric, or small bowel surgery
- Prior history of inflammatory bowel disease
- Concern for infectious colitis
- Non-English speaking
- Evidence of dysphagia at the time of presentation
- Presence of bright red blood per rectum
- Allergy to metoclopramide or erythromycin
- Code status of DNR/DNI or CMO
- Prior history of abdominal radiation
- Presence of ICD or pacemaker or other implanted electronic devices
- Abdominal pain suggesting an acute abdomen or obstruction. In clinical practice, only patients with crampy abdominal pain due to

INVESTIGATOR STUDY PLAN - REQUIRED

Crohn's disease, previous intestinal surgery and a previous history of radiation therapy require a patency capsule or CT enterography before capsule endoscopy.

- Patients who cannot undergo surgery

6) Study-Wide Number of Subjects*

Not applicable – not a multi-site study

7) Study-Wide Recruitment Methods*

Not applicable – not a multi-site study

8) Study Timelines*

1. The participation of individual subjects in this study will be approximately 31-40 days (the length of their hospitalization plus an additional thirty days for follow up).
2. The duration anticipated to enroll all study subjects is about 24 months.
3. The estimated date for the investigators to complete this study and data analysis is two years.

9) Study Endpoints*

The primary endpoint will be time to diagnosis. Secondary endpoints will include hospital length of stay, number of invasive procedures, blood product transfusions.

10) Procedures Involved*

Screening

Patients presenting to the Emergency Room with NHGIB (defined as melena or hematochezia) will be identified by a member of the ED staff.

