Depending on the findings a recommendation will be made as to the next most appropriate test. See attached Figure 1. If blood is found in the esophagus, stomach or duodenum an upper endoscopy is recommended. If blood is seen in the small intestine, it will be recommended that the subject next have a push enteroscopy, deep enteroscopy, or angiography. If blood in right colon, colonoscopy may be performed or deferred to colonoscopy as an outpatient, if active bleeding has ceased. If the capsule study is not diagnostic and no blood is seen in the GI tract and there is no ongoing hematochezia, the subject will be placed in ED observation for up to 23 hours and evaluated for potential discharge and follow-up by gastroenterology as an outpatient.

INVESTIGATOR STUDY PLAN - REQUIRED

If no bleeding/ blood or a likely source is found. These individuals will be considered for observation, early discharge and follow up in the GI outpatient setting.

For most subjects, the capsule will pass in a bowel movement within 24 - 72 hours of ingestion.

An equal number subjects [up to 80] will be randomized to the “conventional workup group”. “Conventional Workup” for NHGIB could include upper endoscopy, colonoscopy, and additional capsule or small bowel enteroscopy depending on the subject’s presentation and the results of the workup performed by the gastroenterology team. For some subjects, the VCE would be done as part of standard of care estimated that 5-15% of patients will have small intestinal bleeding. For patients requiring a video capsule endoscopy as part of “conventional workup” the patients will be given the same Olympus video capsule that is used in the “Early Capsule” group. Further management would be as standard of care. These subjects will be discharged on the recommendation of the attending hospitalist after completion of treatment.

Review and Follow-Up

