During hospitalization, data will be recorded from ED pulse check, Meditech, Soarian, and Allscripts regarding fluid administration, transfusion of pRBC, initial hematocrit, times and types of procedures (e.g. upper endoscopy, enteroscopy, colonoscopy), time from entry to ED to time to diagnosis (i.e. localization of source of bleeding), admission disposition (i.e. clinical decision unit, regular floor, ICU), time of discharge. The procedures involved in the hospitalization (i.e. upper endoscopy, enteroscopy, and colonoscopy) will be done as part of standard of care. All of this information will be linked to the subject’s study ID number as described above. This data collection is for research purposes only.

In addition, the costs of the procedures will be collected through financial services. The costs that will be collected are both the fixed and variable costs associated with each patient in the study. We will also collect the direct and indirect costs allocated to each patient. All charges associated with the admission for each patient in the study will have costs allocated. This will be evaluated as an additional data point to compare the two arms of the study. No additional PHI will be collected.

Telephone Follow-Up

Subjects will also be contacted by phone by a research staff member at two different time points following their discharge from the hospital. These time points will be at 3 days (+2 days) and 30 days (+/- 3 days) following their discharge. At these time points a staff member will call a subject to obtain information about whether or not a patient has had recurrent bleeding and whether or not the patient had to be readmitted to a hospital or emergency room for

INVESTIGATOR STUDY PLAN - REQUIRED

recurrent bleeding. Please see attached form for telephone script that staff member will read along with particular questions that will be asked.

No more than three attempts will be made at each time point to reach the subject. If a message is left, it will be "Hello, this is [name] calling from UMass looking to speak with [subject]. Please call back at [number] at your earliest convenience. Thank you."

11) Data and Specimen Banking*

N/A – no data banking.

12) Data Management*

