PUBLISH DATE JUNE 20, 2018

STATISTICAL ANALYSIS PLAN

TITLE: A comparison of early deployment of a video capsule (Endocapsule EC-10: Olympus Tokyo. Japan) in the Emergency Department versus conventional work-up of non-hematemesis gastrointestinal bleeding [NHGIB].

NCT02442830

[name], PHD, PRINCIPAL INVESTIGATOR

STATISTICAL ANALYSIS PLAN

Study outcomes:

The primary outcome for this study was the rate of localization of bleeding during hospitalization. Localization of bleeding was defined as identification of blood or identification of a lesion with high-risk stigmata of recent hemorrhage (SRH). Secondary outcomes included, overall rate of localization of bleeding by the end of admission, anatomic location of bleeding or the bleeding source, rate of endoscopic therapy, rate of readmission, rate of diagnosis of vascular lesions (defined as Dieulafoy's lesions or angioectasias), rate of re-bleeding within 30 days of discharge, rate of all-cause mortality within 30 days of hospitalization, cumulative direct hospital costs by the end of admission, and overall rate of identifying the etiologic diagnosis.

Sample size calculation:

The study was planned as a superiority trial and the estimated probability of localization of bleeding during hospitalization in the Early Capsule arm to be two times greater than that of the Standard of Care arm (i.e. estimated hazard ratio of 2.00). We found no prior studies similar to our methodology, so prior experience at our institution guided the estimation of effect. Power analysis revealed that for this effect size to be detected (80% chance) as significant at the 5% level, a sample of at least 72 patients (36 per group) would be required.

Statistical analysis:

Patient characteristics were described as means with standard deviation (SD) or as proportions. Time to localization and time to first procedure were described using medians with interquartile range (IQR). Hospital costs were described in US dollars (USD).

Independent variables selected for analysis included those previously suggested as prognostic indices for NHGIB. Variables chosen for analysis included gender, race, age, vital signs at admission, use of anticoagulants, use of non-steroidal anti-inflammatory drugs (e.g. aspirin and ibuprofen; NSAIDs), use of a P2Y₁₂ inhibitor (e.g. clopidogrel), factors that contribute to the Glasgow-Blatchford Score, and type of bleeding at admission (i.e. hematochezia, melena, or symptomatic anemia).

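### Read literally, the withdrawal rule covers a confirmed esophageal source, which the same protocol treats as in scope and which meets the primary outcome

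*Protocol*

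**What the plan says.** Protocol section 14 (Withdrawal of Subjects) sets an anatomical limit: "Patients will be withdraw from study if the bleeding source is found to be outside of the stomach or intestines". It makes no exception for the esophagus.

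Other parts of the plan place the esophagus inside the study:

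- Protocol section 4 (Background) describes the capsule as "able to visualize bleeding in the esophagus, stomach, duodenum, small intestine and right colon".
- Protocol section 10 (Procedure) gives esophageal blood its own next step: "If blood is found in the esophagus, stomach or duodenum an upper endoscopy is recommended".
- Protocol section 5 admits patients by presentation, "New onset of melena or hematochezia". It excludes dysphagia at presentation but not an esophageal source.

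The outcome definitions carry no site limit:

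- Protocol section 9: "The primary endpoint will be time to diagnosis". Section 10 (Review and Follow-Up) explains this as "time to diagnosis (i.e. localization of source of bleeding").
- SAP, Study outcomes: "Localization of bleeding was defined as identification of blood or identification of a lesion with high-risk stigmata of recent hemorrhage (SRH"). The SAP also makes anatomic location a secondary outcome.

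The SAP does not mention the withdrawal rule. Neither document defines an analysis population or says how withdrawn patients enter the analysis.

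**The concern.** The rule applies after randomization and is triggered by the outcome itself. It can act only once a source has been found. Among esophageal bleeds it can therefore take out localized patients and never unlocalized ones. Any handling that removes or recodes these patients lowers the localization rate and empties the esophageal row of the anatomic-location outcome.

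This differs from the general question of which patients are analysed. A statement that all randomized patients are analysed would protect the rates, but section 14 would still conflict with the pathway in section 10.

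**Working it through.** **Textual check.** Apply the rules to three possible records.

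| Record | Localization under the SAP | Section 14, read literally |
|---|---|---|
| Early capsule arm: blood in esophagus on capsule, esophageal source confirmed at upper endoscopy | Event | Withdrawn |
| Conventional arm: esophageal lesion with high-risk stigmata at upper endoscopy | Event | Withdrawn |
| Either arm: gastric ulcer with high-risk stigmata | Event | Retained |

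The first two rows are the conflict. The trigger is the source, not the blood: blood seen in the esophagus with a source in the stomach does not lead to withdrawal.

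**The plan's own figure.** The point does not rest on a figure in the plan, but the SAP's sample size is needed for scale. Freedman's formula with hazard ratio 2.00, two-sided 5% (sidedness assumed) and 80% power gives (1.960 + 0.842)² × ((1 + 2)/(1 − 2))² = 7.849 × 9 = 70.6. That is 71 events, or 72 as an even total. So 72 is reproduced if every patient has an event.

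**Inputs for the size of the effect.**

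- Capsule yield p₁ = 26/36 = 72.2% (protocol section 4).
- Upper endoscopy yield p₀ = 52.9% (protocol section 4).
- Esophageal share of localized patients, e: not in the documents. Assumed 2% to 15%, the same in both arms.

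The yields are rough stand-ins for arm-level localization rates.

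**Patients affected** = n per arm × (0.722 + 0.529) × e.

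| e | 36 per arm | 80 per arm |
|---|---|---|
| 2% | 0.9 | 2 |
| 5% | 2.3 | 5 |
| 10% | 4.5 | 10 |
| 15% | 6.8 | 15 |

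**Rates under each handling, e = 10%.** The starting difference is 72.2 − 52.9 = 19.3 points.

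1. Dropped, p(1 − e)/(1 − pe): 0.6498/0.9278 = 70.0% and 0.4761/0.9471 = 50.3%. Difference 19.8 points.
2. Censored at localization in Kaplan-Meier, 1 − (1 − p)^(1 − e), assuming the same timing for all sources: 1 − 0.278^0.9 = 68.4% and 1 − 0.471^0.9 = 49.2%. Difference 19.2 points. Both hazards are multiplied by 0.9, so the hazard ratio does not move.
3. Scored as non-events, p(1 − e): 65.0% and 47.6%. Difference 17.4 points.

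**Range over the assumed shares.**

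| e | Dropped (difference) | Censored (difference) | Non-event (difference) |
|---|---|---|---|
| 2% | 71.8% v 52.4% (19.4) | 71.5% v 52.2% (19.3) | 70.8% v 51.8% (18.9) |
| 15% | 68.8% v 48.8% (20.0) | 66.3% v 47.3% (19.0) | 61.4% v 45.0% (16.4) |

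**Power.** With all 72 patients having events, Freedman power is Φ(√72/3 − 1.960) = 80.7%. Losing 10% leaves 64.8 events, and Φ(√64.8/3 − 1.960) = 76.5%. The protocol's own comparison of means, at 80 per arm, keeps power above 99.9%.

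**The case against.** The strongest reply is that this is one loose noun phrase with no documented consequence. Several parts of that reply stand.

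- A reader might infer that esophageal cases are left out of the analysis. The documents do not say so. A withdrawn patient's localization time could still be analysed, and if all randomized patients are, the loss in the rates and the location outcome disappears.
- A reader might infer that withdrawal ends the 30-day follow-up for re-bleeding, readmission and mortality. Section 14 does not say this. Section 10 schedules the calls without excluding withdrawn patients, and in-hospital data come from medical records.
- The rule may have been aimed at sources outside the gastrointestinal tract, and staff working from the section 10 pathway may have applied it that way. That is plausible, but neither document states the intent or shows how the rule was applied.
- The stand-in yields fit poorly. Section 4 says capsules often followed negative upper endoscopy and colonoscopy, so that group had often been screened for esophageal sources already. The 52.9% is the yield of one test in a cohort with any gastrointestinal bleeding, not of a whole conventional work-up.

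These points limit what can be claimed about size and consequence. They do not remove the contradiction: followed as written, section 14 withdraws patients whom section 10 keeps in the pathway and whom the SAP counts as localized.

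**Conclusion.** The contradiction holds on the text. A confirmed esophageal source satisfies the primary outcome under either document and, at the same moment, triggers a withdrawal after randomization that depends on the outcome. Whether valid localizations are then lost depends on a handling rule that neither document gives.

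If they are lost, and 10% of localized patients have an esophageal source, each arm's rate falls by about 2 to 7 points: the capsule stand-in by 2.2 to 7.2 and the endoscopy stand-in by 2.6 to 5.3. The share is assumed and the yields are stand-ins, so these figures show scale and are not estimates.

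A reader might infer that the rule biases the comparison towards one arm. The documents do not support that. It applies to both arms, the difference moves from 19.3 to between 17.4 and 19.8 points at the 10% share depending on handling, and the true direction depends on how often each arm finds such sources. The matter should be corrected because the fix is cheap and the affected outcomes include the primary one, not because the treatment contrast is in doubt.

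**What to change.** 1. Reconcile protocol section 14 with sections 4 and 10 and with the SAP's Study outcomes, so that the withdrawal boundary matches the sites the study treats as in scope.
2. State in the SAP that a localized esophageal source is a localization event at its time of identification, with the site recorded as esophagus.
3. Check the withdrawal log for patients withdrawn under the literal wording, and restore event, time and site from data already collected. Section 10 already provides for recording procedure times and time to diagnosis.

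Timing matters for the third step. Protocol section 12 has the identifier keys destroyed once primary analysis is complete, and the SAP, dated June 2018, is written in the past tense. If linkage is gone, report the number of such withdrawals and how they were handled.

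The cost is a sentence in each document, a check of the log and re-abstraction of a few records. No patients or procedures are added.
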